11.4 MEDICAL HISTORY

Medical history will be captured at the Screening visit. Medical history will be coded using MedDRA and will be summarized by MedDRA system organ class and preferred term for the Safety population.

11.5 EXTENT OF EXPOSURE

The dose (mg) of study drugs administered, the total number of doses of study drugs, and the duration of treatment (number of study cycles) will be summarized with descriptive

UTX-TGR-208

Version 2.0 Dated: 30 July 2020

statistics. The number and percentage of subjects whose dose is modified at any time will be summarized by each type of modification by cycle and overall. The proportion of subjects completing each cycle of treatment will be summarized.

11.6 EFFICACY ANALYSES

Each subject will be assigned to one of the following categories: undetectable minimal residual disease or detectable minimal residual disease.

Further, response will be categorized as 1) complete response, 2) partial response, 3) stable disease, 4) progressive disease, 5) early death from malignant disease, 6) early death from toxicity, 7) early death because of other cause, or 9) unknown (not assessable, insufficient data).

Many of the efficacy measures will be based on disease assessments. The best clinical response as well as disease progression will be determined by the treating clinician. Definitive disease progression will be based on standard criteria (Hallek, et al., 2018) occurring for any reason (e.g., increasing lymphadenopathy, organomegaly or bone marrow involvement; decreasing platelet count, hemoglobin, or neutrophil count; or worsening of disease-related symptoms) other than lymphocytosis.

11.6.1 STATISTICAL ANALYSES

11.6.1.1 PRIMARY EFFICACY ENDPOINT

Best overall U-MRD rate will be reported as well as a proportion during cycles 3, 6, 9, 12, 15, 18, 21 and 24. The U-MRD rate is defined as the proportion of subjects with detectable MRD at baseline who convert to U-MRD in the peripheral blood on two sequential peripheral blood studies at least 4 weeks apart post-baseline. Subjects with detectable MRD at baseline who do not have an MRD assessment at any post-baseline visits will be considered non-responders and will be included in the denominator when calculating U-MRD rate. The 95% confidence intervals (Clopper-Pearson) for the MRD negativity rate will be presented.

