Following screening, qualified subjects will add ublituximab and umbralisib to their existing ibrutinib, acalabrutinib or venetoclax treatment. Any therapy previously given concurrently with ibrutinib, acalabrutinib or venetoclax, including anti-CD20 therapy, must have been discontinued 21 days prior to Day 1 of Cycle 1 (See Exclusion Criterion #1). Determination of enrollment in Cohort A versus Cohort B or Cohort C will depend on which agent the subject was receiving prior to screening (ibrutinib, acalabrutinib or venetoclax).

Three cohorts will be studied:

- **Cohort A:** ublituximab and umbralisib with ibrutinib
- **Cohort B:** ublituximab and umbralisib with venetoclax
- **Cohort C:** ublituximab and umbralisib with acalabrutinib

Up to approximately 28 subjects may be enrolled into each cohort.

Study Duration

MRD status of all subjects will be evaluated during cycles 3, 6, 9, 12, 15, 18, 21, and 24. If subjects achieve U-MRD status in the peripheral blood, MRD will again be assessed by peripheral blood 4 weeks later to confirm U-MRD. Subjects will remain on study treatment through 24 cycles or the occurrence of confirmed U-MRD response in the peripheral blood, after which they will enter a period of treatment-free observation.

Following achievement of U-MRD, subjects will enter a period of treatment-free observation (TFO) with serial MRD assessments every 12 weeks up to Cycle 24 then every 24 weeks thereafter, unless clinically indicated sooner.

Subjects who do not achieve confirmed U-MRD will continue treatment until the completion of 24 cycles of treatment, definitive disease

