Dosing Regimen & Treatment Study Visits	
progression, unacceptable toxicity, or withdrawal from the study due to investigator decision or other reasons. Subjects who complete 24 cycles of treatment and remain D-MRD (MRD positive), or those who discontinue study treatment and have not progressed will enter a period of treatment-free observation. Subjects entering treatment-free observation with D-MRD, no PB MRD assessment is required during TFO.
 
All subjects (whether U-MRD or D-MRD following treatment) who subsequently develop clinical progression requiring treatment per iwCLL criteria (Hallek, et al., 2018) will be retreated with the same triple combination regimen previously received, provided that clinical progression occurs after 6 months of treatment-free observation. Retreatment will not be initiated upon achieving MRD positivity, but only upon clinical progression requiring treatment per iwCLL criteria. Subjects who progress within 6 months of treatment-free observation will be considered refractory and discontinue from the study.
																		
	Cohort A: Ublituximab and Umbralisib with Ibrutinib																		
	Cycle 1:																		
	
  
 Ublituximab	Umbralisib	Ibrutinib			
   
 Day 1	Day 2	Day 8 & 15	Daily	Daily	
 
 150 mg	750 mg	900 mg	800 mg	previously tolerated dose	
  
					Ublituximab	Umbralisib	Ibrutinib			Day 1	Day 2	Day 8 & 15	Daily	Daily	150 mg	750 mg	900 mg	800 mg
Ublituximab	Umbralisib	Ibrutinib																	
Day 1	Day 2	Day 8 & 15	Daily	Daily															
150 mg	750 mg	900 mg	800 mg	previously tolerated dose															
Cycles 2 through 6:																			

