3 OBJECTIVES AND ENDPOINTS

3.1 STUDY OBJECTIVES

PRIMARY OBJECTIVES

- To assess the rate of undetectable minimal residual disease (U-MRD) in subjects with CLL treated with the combination of ublituximab and umbralisib with either venetoclax, ibrutinib or acalabrutinib

SECONDARY OBJECTIVES

- To assess safety and tolerability of ublituximab and umbralisib with venetoclax, ibrutinib or acalabrutinib
- To determine the time to U-MRD at planned sequential response assessments
- To determine progression free survival and time to second objective disease progression, from time of initiation of ublituximab and umbralisib with venetoclax, ibrutinib or acalabrutinib
- To determine the durability of clinical benefit after treatment discontinuation as measured by duration of peripheral blood U-MRD response and treatment-free survival
- To determine the overall response rate, complete response rate, U-MRD rate, and PFS to re-treatment with ublituximab and umbralisib with venetoclax, ibrutinib or acalabrutinib in subjects who progress following achievement of U-MRD followed by treatment-free observation.

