7 STUDY ASSESSMENTS AND TREATMENT SCHEDULES

7.1 STUDY ASSESSMENT AND TREATMENT SCHEDULE - INITIAL TREATMENT

Cycle=28 days	Screen	Cycle 1 ¹				Cycle 2-6 ²	C9 and every 3 cycles through C24 ³	EOS*
Procedure/Days	-28-1	D1	D2	D8	D15	Day 1	Day 1	
Medical History	X							
Rai Staging	X							
ECOG	X	X				X	X	X
Physical Examination	X	X				X	X	X
Vital Signs⁴	X	X	X	X	X	X	X	X
12-Lead EKG	X							
Hematology	X	X	X	X	X	X	X	X
Chemistry	X	X	X	X	X	X	X	
Coagulation Studies	X	X				X	X	
HCV, HBV, CMV⁵	X							
CMV surveillance⁶						C3&6	C9, 12, 15, etc.	
PB MRD⁷	X					X	X	
β₂-microglobulin	X							
Pregnancy Test⁸	X					X	X	
Response assessments¹⁰	X					C3 & C6	C 12, 18 & C24	
AE Evaluation	X	X	X	X	X	X	X	X
Con Meds	X	X	X	X	X	X	X	X
Ublituximab		X	X	X	X	X	X	
Umbralisib						Daily until confirmed U-MRD ¹¹		
Cohort A: Ibrutinib						Daily until confirmed U-MRD ¹¹		
Cohort B: Venetoclax						Daily until confirmed U-MRD ¹¹		
Cohort C: Acalabrutinib						Every 12 hours until confirmed U-MRD ¹¹		

¹ Treatment Administration +/- 1 day window after cycle 1 day 1. Physical Exam, Vital Signs, ECOG PS, Hematology and Serum Chemistry visit days have - 1 day window. All assessments must be completed prior to dosing.

² Treatment Administration +/- 3 day window. Physical Exam, Vital Signs, ECOG PS, Hematology and Serum Chemistry visit days have a - 3 day window during Cycles 2 through 6.

³ Treatment Administration +/- 7 day window. Physical Exam, Vital Signs, ECOG PS, Hematology and Serum Chemistry visit days have a - 7 day window for all cycles after cycle 6

⁴ Vital signs to include temp, BP, HR, respirations and weight (weight only at baseline).

⁵ Serum Virology to include HBsAg, HBc antibody, HCV antibody, CMV IgG and IgM. If HBc antibody is positive, the subject must be evaluated for the presence of HBV DNA by PCR - See Appendix D. If the subject is CMV IgG or IgM positive, the subject must be evaluated for the presence of CMV DNA by PCR. If subject is HCV positive, evaluate HCV RNA.

⁶ CMV surveillance by PCR every 3 cycles while receiving study treatment. In addition, a final CMV test by PCR should be done upon treatment discontinuation if not already done within previous 3 months.

⁷ For initial treatment, MRD analysis (central lab) in peripheral blood (PB) performed within 30 days prior to Cycle 1/Day 1. MRD analysis in PB during cycles 3, 6, 9, 12, 15, 18, 21, and 24. U-MRD in PB during initial treatment must be confirmed in PB 4 approximately weeks later.

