⁹ Serum Virology to include HBsAg, HBC antibody, HCV antibody, CMV IgG and CMV IgM or CMV by PCR. If HBC antibody is positive, the subject must be evaluated for the presence of HBV DNA by PCR - See Appendix D. If the subject is CMV IgG or CMV IgM positive, the subject must be evaluated for the presence of CMV DNA by PCR.

¹⁰ CMV surveillance by PCR every 3 cycles while receiving study treatment. In addition, a final CMV test by PCR should be done upon treatment discontinuation if not already done within previous 3 months.

¹¹ For retreatment, MRD analysis should be done within 30 days of restarting therapy in peripheral blood (PB) then performed Cycles 6, 8, 11, 14, 17, 20, 23, and 26. If U-MRD in PB during retreatment repeat approximately 4 weeks later. If U-MRD confirmed approximately 4 weeks later, discontinue treatment and follow for progression and survival for 24 months.

¹³ For women of childbearing potential: Serum pregnancy test within 3 days prior to Cycle 1/Day 1; Urine pregnancy tests on Day 1 of each treatment cycle +/- 7 days.

¹⁴ Radiology assessment should include contrasted CT or MRI imaging of neck, chest, abdomen, and pelvis. Scans to be completed within 30 days prior to Cycle 1/Day 1.

¹⁵ Re-treatment subjects – radiology and response assessment within 14 days of Cycles 7, 14, 20, 26 then every 12 months thereafter. At the time of response assessment, bone marrow to be performed as per standard of care if other criteria for complete remission are met. CR should only be confirmed once by bone marrow assessment at planned response assessments.

¹⁶ Response Assessment to be done as per SOC to determine progression-free survival

¹⁷ For subjects being re-treated with venetoclax only. Refer to section 8.3.5.1

¹⁸ Ublituximab Cycle 3 Days 1,2, 8 & 15; Cycle 4-8 Day 1 then every 3 cycles (C11, C14, C17, C20, C23, C26). No further ublituximab after cycle 26

¹⁹ When starting retreatment, dose of umbralisib is at the investigator's discretion, previously tolerated dose should be considered.

²⁰ When starting retreatment, dose of ibrutinib or acalabrutinib is at the investigator's discretion, previously tolerated dose should be considered.

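### The primary U-MRD rate has no end of window, so a first conversion on re-treatment can count; its confirmation interval is also stricter than the one that stops treatment.

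*Combined protocol and SAP*

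**What the plan says.** **Primary definition.** Section 11.6.1.1 takes subjects with detectable MRD at baseline and counts those "who convert to U-MRD in the peripheral blood on two sequential peripheral blood studies at least 4 weeks apart post-baseline". On reporting it says: "Best overall U-MRD rate will be reported as well as a proportion during cycles 3, 6, 9, 12, 15, 18, 21 and 24". It names no last cycle, study phase or cut-off date for the best overall figure. The endpoint definition in Section 3.2 sets no window either, and Section 11.6 assigns each subject to U-MRD or D-MRD without a time point.

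**Initial-treatment schedule.** Synopsis, Study Duration: "MRD status of all subjects will be evaluated during cycles 3, 6, 9, 12, 15, 18, 21, and 24". Section 7.1, footnote 7, adds: "U-MRD in PB during initial treatment must be confirmed in PB 4 approximately weeks later". Under footnote 11, treatment ends with the 28-day cycle in which U-MRD is confirmed.

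**Re-treatment.** The Synopsis (Study Duration) opens re-treatment after later progression to "All subjects (whether U-MRD or D-MRD following treatment"), provided progression comes after 6 months off treatment. Section 7.3, footnote 11, requires MRD testing before restart, "then performed Cycles 6, 8, 11, 14, 17, 20, 23, and 26", with a repeat about 4 weeks after an undetectable result.

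**Secondary objective.** Section 3.1: "To determine the overall response rate, complete response rate, U-MRD rate, and PFS to re-treatment with ublituximab and umbralisib" (plus the partner drug) "in subjects who progress following achievement of U-MRD followed by treatment-free observation".

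**The concern.** The primary estimate should say how often adding ublituximab and umbralisib, for an initial course of up to 24 cycles, converts detectable MRD. Two features of the wording loosen that link.

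First, with an open window, a subject who stays detectable through the initial course, progresses, is re-treated and then converts satisfies the definition. The result could then depend on when the data are cut.

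Second, the rule that stops treatment and the rule that counts a responder use different intervals. The trial can therefore treat a subject as a confirmed responder whom the primary analysis does not recognise.

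In an open-label study, the choice between the literal and the intended reading would be made with results in view.

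**Working it through.** The plan states no target rate, null rate or power (Section 11.1 contains none), so there is no figure to reproduce. The check compares the rules and then sizes the effect.

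**1. Is the window closed anywhere?** In 11.6.1.1 the cycle list governs the by-cycle proportions, which are reported in addition to the best overall rate; it does not bound the latter. The document does close windows elsewhere. Best overall tumour response (10.3) runs to progression or recurrence, and treatment-free survival (11.6.1.2.8) is tied to initial study treatment.

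**2. Who can add to the numerator on re-treatment?** Subjects already counted as confirmed responders add nothing. Only those not yet counted can, chiefly subjects still D-MRD after initial treatment. The Synopsis (Study Duration) admits them to re-treatment, and Section 5.4 is compatible with that. The Synopsis rationale and Section 5.2 instead describe re-treatment with the regimen that produced the initial U-MRD response. These statements conflict.

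**3. When could it happen?** Inputs: 28-day cycles, 24 initial cycles, 6 months off treatment (taken as 183 days), and a first on-treatment re-treatment MRD test at Cycle 6, five cycles after restart.
- First test: 24×28 + 183 + 5×28 = 672 + 183 + 140 = day 995; 995/30.44 = 32.7 months.
- Confirmation 28 days later: day 1023, or 33.6 months.
- Cycle 26 test: 672 + 183 + 25×28 = day 1555, or 51.1 months.
- Extreme case, toxicity stop after one cycle: 28 + 183 + 140 = day 351, or 11.5 months.

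**4. Confirmation interval.** The primary definition needs at least 28 days between samples. Section 7.1 allows about 4 weeks and gives no tolerance. A pair 26 days apart therefore stops treatment but fails as a pair. Under Section 7.2, U-MRD subjects in observation are sampled about every 12 weeks. If the next sample is undetectable, it and the day-26 sample form a qualifying pair, provided off-treatment samples count, which 11.6.1.1 does not say. If MRD has returned, or no sample is taken, the subject does not qualify.

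**5. Size at n = 28** (Synopsis: up to about 28 per cohort). One subject is 1/28 = 3.6 points. Clopper-Pearson limits: lower = Beta quantile(0.025; x, n−x+1); upper = Beta quantile(0.975; x+1, n−x). Responder counts are assumed.

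| Responders | Rate | 95% CI |
|---|---|---|
| 15/28 | 53.6% | 33.9-72.5 |
| 16/28 | 57.1% | 37.2-75.5 |
| 17/28 | 60.7% | 40.6-78.5 |
| 18/28 | 64.3% | 44.1-81.4 |

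From 16 initial responders, one or two re-treatment conversions give the last two rows; one early-confirmed subject who is not rescued gives the first.

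**6. Range for the re-treatment route.** Added points = (1 − initial rate) × share of D-MRD subjects re-treated × share of those converting. All three inputs are assumptions.
- Low: 0.7 initial rate, 0.1, 0.2: 0.3×0.1×0.2 = 0.6 points.
- Middle: 0.5 initial rate, 0.3 re-treated, 0.2 to 0.5 converting: 3.0 to 7.5 points.
- High: 0.3 initial rate, 0.5, 0.5: 0.7×0.5×0.5 = 17.5 points.

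**The case against.** The best defence is that the intent is plain. The cycles in 11.6.1.1 are exactly the initial-treatment MRD schedule, the re-treatment schedule is a different list, and re-treatment U-MRD has its own secondary objective. Initial treatment is capped at 24 cycles, subjects entering observation with D-MRD need no MRD tests, and those who progress within 6 months leave the study. This largely stands as evidence of intent, and it limits how often and how early the problem can arise. It does not close the window, because no sentence excludes re-treatment samples.

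A reader might infer three stronger things that the documents do not support:
- *That re-treatment conversions are planned to count and will raise the result.* Nothing says so. They can count under a literal reading.
- *That one conversion counts in both the primary and the re-treatment endpoint.* The secondary objective covers only subjects who had already achieved U-MRD. If that was confirmed under 11.6.1.1, they are already in the primary numerator. Overlap is possible only for a subject whose initial U-MRD missed the 4-week minimum. The real gap is different: a D-MRD subject's first conversion on re-treatment belongs to no secondary objective.
- *That every subject confirmed a few days early is lost.* A later undetectable sample in observation can rescue the subject, as step 4 shows.

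**Conclusion.** The point holds in a limited form and should be corrected. The best overall U-MRD rate has no stated end, so a first confirmed conversion on re-treatment can enter it. After a full initial course this is a concern only for data cuts from about month 33. The mismatch between the stopping rule and the counting rule can work in the opposite direction and does not depend on a late cut.

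Each affected subject is worth 3.6 points at 28 per cohort. That is small beside an interval about 38 points wide (37.2 to 75.5 at 16/28), but it is avoidable in the primary endpoint. The responder counts and re-treatment shares are illustrations, as the documents give none. The re-treatment route also depends on D-MRD subjects being eligible for it, on which the document disagrees with itself.

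**What to change.** 1. **Close the window (11.6.1.1, 3.2 and Synopsis).** Count only samples from Cycle 1 Day 1 through the confirmatory sample of the initial course, at the latest the one for Cycle 24, and before any re-treatment or other anti-CLL therapy. State that the TFO1 sample and its 4-week repeat after a toxicity stop (Section 7.2) are included.
2. **Use one confirmation interval, with the same tolerance, in 7.1 and 11.6.1.1,** so that every subject stopped for confirmed U-MRD counts as a responder. This must accompany item 1: closing the window alone would remove the later observation sample that can rescue an early-confirmed subject.
3. **Report re-treatment conversions separately,** including those in subjects who were D-MRD after initial treatment. Reconcile the Synopsis rationale and Section 5.2 with the Synopsis Study Duration text on who is re-treated.

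The cost is a few sentences, with no new visits or samples. The downside is a rate that may be slightly less favourable at late data cuts.

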5.4 RETREATMENT PHASE

Study Schema for Re-Treatment

*Progression Of Disease (PD) – Defined per the iwCLL Criteria (Hallek 2018)
U2 – ublituximab and umbralisib; IB – ibrutinib; ACALA – Acalabrutinib; VEN – venetoclax; MRD – minimal residual disease; EOS – end of study

Subject on treatment-free observation who subsequently develop clinical progression requiring treatment per iwCLL criteria (Hallek, et al., 2018) after 6 months of treatment-free observation will be retreated with the triple combination regimen that was previously received. Subjects who progress within 6 months of treatment-free observation discontinue from the study.

For subjects enrolled in Cohort A, retreatment will consist of 2 cycles of ibrutinib followed by treatment with ublituximab and umbralisib with ibrutinib cycles 3 through 26 of retreatment. The previously tolerated ibrutinib dose should be considered but is at investigator discretion (maximum dose 420mg daily).

For subjects enrolled in Cohort B, venetoclax should be initiated per the package insert. The target ramp-up dose should be considered based on the previously tolerated dose but is at investigator discretion (maximum dose 400mg daily). Retreatment will consist of 2 cycles of venetoclax followed by treatment with ublituximab and umbralisib with venetoclax cycles 3 through 26.

For subjects enrolled in Cohort C, retreatment will consist of 2 cycles of acalabrutinib followed by treatment with ublituximab and umbralisib and acalabrutinib cycles 3 through 26 of retreatment. The previously tolerated acalabrutinib dose should be considered but is at the investigator discretion.

Clinical response and U-MRD rate will be studied upon retreatment. If subjects achieve U-MRD status in the peripheral blood, MRD will be assessed by peripheral blood 4 weeks later to confirm U-MRD. Retreatment will continue until the occurrence of confirmed U-MRD response in the peripheral blood, completion of 26 cycles (24 cycles of triplet therapy), UTX-TGR-208

Version 2.0 Dated: 30 July 2020

definitive disease progression, unacceptable toxicity, or withdrawal from the study due to investigator decision or other reasons. Subjects who discontinue study treatment and have not progressed will continue to be followed for disease progression.

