⁸ For women of childbearing potential: Serum pregnancy test within 3 days prior to Cycle 1/Day 1; Urine pregnancy tests on Day 1 of each treatment cycle +/- 7 days.

¹⁰ Radiology assessment should include a contrasted CT or MRI imaging of neck, chest, abdomen, and pelvis. For initial treatment, scans to be completed within 30 days prior to Cycle 1 / Day 1. All tumor evaluations post baseline assessment should be performed within 14 days of cycles 3, 6, 12, 18 and 24.. Follow up CTs to be done at investigator discretion/ per standard of care. At the time of response assessment, bone marrow to be performed as per standard of care if other criteria for complete remission are met. CR should only be confirmed once by bone marrow assessment at planned tumor assessments.

¹¹ If U-MRD is confirmed, subjects will complete treatment through the end of that 28-day cycle then return for their first TFO at the subsequent Cycle.

***EOS = End of Study** – EOS visit occurs if subject is discontinuing from the study. Please see Section 5.6 Discontinuation from study , which outlines reasons subject must discontinue from study.

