7.2 STUDY ASSESSMENT AND TREATMENT SCHEDULE - TREATMENT FREE OBSERVATION

Cycle = 28 days	Treatment-Free Observation (TFO) Visits ¹	
Procedures/Days ²	TFO1 Cycle 1 Day 1	TFO Subsequent Day 1 Every 3 Cycles for 24 cycles and every 6 cycles thereafter
ECOG	X	X
Physical Examination	X	X
Vital Signs ³	X	X
Hematology	X	X
Chemistry	X	X
PB MRD ⁴		X
AE Evaluation	X	X
Con Meds	X	X

¹ At completion of 24 cycles with no progression of disease (POD), confirmed U-MRD, or discontinuation of treatment due to toxicity in absence of POD, subjects will enter a treatment-free observation period. Study assessments will be completed every 3 cycles for 24 cycles from discontinuation of any study drug.

² All TFO visits have a +/- 14 day window.

³ Vital signs to include temp, BP, HR, and respirations

⁴ Subjects on treatment-free observation with U-MRD should have peripheral blood MRD assessments approximately every 12 weeks +/- 2 weeks prior to Cycle 24 and every 24 weeks +/- 2 weeks, unless clinically indicated sooner, after Cycle 24. For subjects entering treatment-free observation with D-MRD, no PB MRD is required. For subjects entering TFO due to discontinuation of treatment due to toxicity in absence of POD, MRD should be done at TFO1. If U-MRD repeat MRD in PB in 4 weeks, if D-MRD, no further PB MRD is required.

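### The primary U-MRD rule needs samples at least 4 weeks apart, but the confirmatory draw is only nominally at 4 weeks, so a slightly early draw stops treatment on a pair that the primary analysis does not count

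*Combined protocol and SAP*

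**What the plan says.** **Primary rule.** Section 11.6.1.1 bases the U-MRD rate on those whose baseline MRD was detectable. To be responders, they must "convert to U-MRD in the peripheral blood on two sequential peripheral blood studies at least 4 weeks apart post-baseline". It reports the best overall rate and the proportions at cycles 3 to 24, with Clopper-Pearson intervals.

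**Confirmatory draw.** The synopsis (Study Duration) says that after a first U-MRD result "MRD will again be assessed by peripheral blood 4 weeks later to confirm U-MRD". Section 7.1, footnote 7, says "U-MRD in PB during initial treatment must be confirmed in PB 4 approximately weeks later" (word order as printed).

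**Windows.** Section 7.1, footnote 3, says "Physical Exam, Vital Signs, ECOG PS, Hematology and Serum Chemistry visit days have a - 7 day window for all cycles after cycle 6". Footnotes 1 and 2 give shorter windows for the same assessments. None of the three lists MRD.

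**Stopping.** Section 5.2 ends treatment on confirmed U-MRD. Section 7.1, footnote 11, adds: "If U-MRD is confirmed, subjects will complete treatment through the end of that 28-day cycle", after which observation begins. Neither states a minimum gap between the two samples.

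**After stopping.** Section 7.2, footnote 4, says "Subjects on treatment-free observation with U-MRD should have peripheral blood MRD assessments approximately every 12 weeks +/- 2 weeks prior to Cycle 24". The Section 7.2 table marks no MRD sample at the first observation visit.

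**Related definitions.** Section 3.2 defines the U-MRD rate by central-lab confirmation, without a two-sample or 4-week condition. Section 11.6.1.2.1 times U-MRD to the first undetectable assessment. Section 11.6.1.2.7 analyses duration among subjects with a U-MRD response and does not say that the response must be confirmed.

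**The concern.** The analysis has a one-sided floor of 28 days between samples. The schedule aims at that same 28 days, and footnote 7 allows variation on either side of it. A site that draws on day 26 has followed footnote 7. The subject counts as confirmed and leaves treatment, yet those two samples do not satisfy the primary definition.

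Section 11.6.1.1 has an explicit non-responder rule only for subjects with no post-baseline MRD assessment. It is silent on a short-gap pair, so such a subject is a non-responder simply by not meeting the definition. Two subjects with identical MRD results can then be classified differently because of a few days in the draw date. In an open-label trial, an unresolved rule of this kind may be settled only after the results are known.

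**Working it through.** The plan offers no figure to reproduce: Section 11.1 gives no null rate, target rate, alpha or power. The check is a comparison of rules, followed by a sensitivity calculation.

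**Step 1: the two rules at the same gap.** Let *d* be the days between the first U-MRD sample and the confirmatory one. The primary rule requires *d* ≥ 28 (4 × 7). The stopping rule has no stated minimum.

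| *d* | Confirmed for stopping (footnotes 7 and 11) | Pair counts in Section 11.6.1.1 |
|---|---|---|
| 26 | yes, approximately 4 weeks | no, 26 < 28 |
| 28 | yes | yes |
| 30 | yes, approximately 4 weeks | yes |

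The rules disagree only for draws before day 28.

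**Step 2: can an early-draw subject still qualify?** Section 11.6.1.1 asks only for post-baseline samples, so a later one can complete a pair. Example, ignoring laboratory turnaround and visit windows: the first sample is on Day 1 of a cycle (day 0) and the second on day 26. The cycle ends and observation starts on day 28. The next MRD sample is due 12 ± 2 weeks later, that is 10 to 14 weeks or 70 to 98 days, which is day 98 to 126. The gap from the second sample is 98 − 26 = 72 to 126 − 26 = 100 days, so the spacing condition is met. If that third sample is undetectable, samples two and three form a qualifying pair. If it is detectable or missing, these samples contain no qualifying pair.

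Final misclassification therefore needs two events: an early draw, and no undetectable result at the first treatment-free MRD sample.

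**Step 3: weight of one subject.** The synopsis allows up to about 28 subjects per cohort, so one subject is 1/28 = 3.6 percentage points. The Clopper-Pearson limits are the 0.025 quantile of Beta(*x*, *n* − *x* + 1) and the 0.975 quantile of Beta(*x* + 1, *n* − *x*). For illustrative counts:

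| Responders | Rate | 95% CI | Width |
|---|---|---|---|
| 15/28 | 53.6% | 33.9% to 72.5% | 38.6 points |
| 14/28 | 50.0% | 30.6% to 69.4% | 38.7 points |

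**Step 4: expected loss, on assumptions.** Let *X* be the number confirmed for stopping, *s* the share of early draws, and *r* the share of those without an undetectable first treatment-free sample. The expected loss is *X* × *s* × *r*. The documents give none of these. Assume *X* = 14.

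| *s* | Loss if *r* = 0 | Loss if *r* = 1 | Effect on rate if *r* = 1 |
|---|---|---|---|
| 5% | 0 | 0.7 subjects | 0.7/28 = 2.5 points |
| 10% | 0 | 1.4 subjects | 1.4/28 = 5.0 points |
| 20% | 0 | 2.8 subjects | 2.8/28 = 10.0 points |

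The *r* = 1 columns are upper limits for each *s*.

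**Step 5: consistency with the other endpoints.** A single undetectable result that is never confirmed is an event under Section 11.6.1.2.1 and a non-response under Section 11.6.1.1. Section 3.2 could count it either way.

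**The case against.** The strongest reply is that the texts are compatible. A draw on day 28 or later satisfies all of them, and a site can draw on day 28 as easily as on day 26. An early-draw subject is not lost if the first treatment-free sample is still undetectable. No decision hangs on the rate, because the cohorts are estimated separately, with wide intervals and no threshold. All of this stands, and it limits the size of the point. It does not remove the mismatch: an early draw is compliant with footnote 7, and the second chance turns a question about response into one about durability off treatment, which Section 11.6.1.2.7 measures separately.

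A reader might infer more than the documents support:

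- **That every early draw is a lost responder.** Section 11.6.1.1 has no on-treatment requirement, so this does not follow.
- **That the rate could fall by about half.** If draws were spread evenly by day over ±3 or ±7 days around day 28, 3/7 = 43% or 7/15 = 47% would be early, and 14/28 would become 8/28 = 29% or about 7.5/28 = 27%. This borrows windows that the protocol does not apply to MRD and counts no later sample.
- **That re-treatment has the same defect.** Section 11.6.1.1 names only cycles 3 to 24 of initial treatment. The plan does not say that its rule governs the re-treatment rate.

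**Conclusion.** The inconsistency holds and is minor. As written, a confirmatory draw shortly before day 28 confirms U-MRD for stopping treatment, but the pair fails the primary definition. The subject's primary classification then depends on the first treatment-free MRD sample.

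Confidence in the wording mismatch is high. Its effect is unknown and probably small, because two events must coincide. Each subject finally misclassified costs 3.6 points in a cohort of 28, against an interval about 39 points wide. The counts and the shares in the expected-loss calculation are assumptions. The conclusion takes footnote 7 at its word and takes Section 11.6.1.1 to accept any post-baseline sample.

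**What to change.** Before results are reviewed:

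1. In Section 11.6.1.1, define the primary pair as the same two consecutive central-lab U-MRD samples that the protocol uses to confirm U-MRD. Replace the bare 4-week floor with a tolerance equal to the MRD draw window that the sponsor specifies.
2. Date the response at the first sample of the pair.
3. Use this confirmed definition in Sections 3.2, 11.6.1.2.1 and 11.6.1.2.7, so that an unconfirmed single result is not an event for time to U-MRD while being a non-response in the primary analysis.
4. Reconcile the synopsis (Study Duration), Section 7.1 footnotes 7 and 11, and Section 11.6.1.1.

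The cost is protocol and SAP wording, with no new samples or subjects. No minimum interval for the draw is proposed, because that could change when treatment stops and could require repeat samples. The stopping rule stays with the sponsor.
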